4.2.5 Suicidal Behavior and Suicidal Ideation

Evaluations of suicidality should be completed similar to how it is described in the protocol.

If suicidal ideation or behavior is reported, conduct further risk evaluation as per typical procedures and follow site processes and utilize emergency services or crisis lines, as needed. The medical monitor should be contacted for immediate guidance and support.

Confidential - Proprietary Information

18

5 Investigational Medicinal Product

Given the ongoing COVID-19 restrictions, clinical sites are permitted to ship IMP directly to subjects.

Confidential - Proprietary Information

This page is a manifestation of an electronically captured signature

SIGNATURE PAGE

Document Name: 405-201-00015 Protocol Addendum

Document Number: CCI

Document Version: 2.0

| Signed by | Meaning of Signature | Server Date (dd-MMM- yyyy hh:min) - UTC timezone |
|-----------|-----------------------------------|---|
| PPD | Clinical Pharmacology Approval | 02-Jun-2020 19:55:58 |
| PPD | Biostatistics Approval | 02-Jun-2020 19:55:56 |
| PPD | Clinical Approval | 02-Jun-2020 18:08:00 |
| PPD | Safety Approval | 03-Jun-2020 03:05:58 |

Until the information herein is released by Otsuka to the public domain, the contents of this document are Otsuka confidential information and should not be duplicated or re-distributed without prior written consent of Otsuka.

## 1 Introduction

This statistical analysis plan (SAP) documents the statistical methodology and data analysis algorithms and conventions to be applied for statistical analysis and reporting of efficacy and safety data of study 405-201-00015. All amendments to the protocol are taken into consideration in developing this SAP.

# 2 Study Objectives

The primary objective of this trial is to assess the safety and tolerability of centanafadine SR tablets administered BID (400 mg TDD) in the treatment of adults with ADHD.

# 3 Study Design

This is a phase 3, 52-week, open-label, multicenter trial to assess the long-term safety and tolerability of centanafadine SR tablets (400 mg TDD) for the treatment of adults with ADHD. The trial population will include male and female subjects 18 to 55 years of age (inclusive) who meet Diagnostic and Statistical Manual of Mental Disorders, Fifth Edition (DSM-5) criteria for ADHD (including predominantly inattentive presentation, hyperactive presentation, and combined presentations) as confirmed by the Adult ADHD Clinical Diagnostic Scale (ACDS) Version 1.2. Subjects who rollover from the double-blind phase 3 trial (i.e., Trial 405-201-00013 or Trial 405-201-00014) and de novo subjects from selected sites are permitted to enroll in this trial.

This trial will have 3 periods for rollover subjects:

- 1. Baseline;
- 2. Open-label treatment; and
- 3. Follow-up.

The trial will have 4 periods for de novo subjects:

- 1. Screening and washout;
- 2. Baseline;
- 3. Open-label treatment; and
- 4. Follow-up.

The trial will be organized as follows:

CI

# Rollover Subjects from Double-blind Phase 3 Trial (i.e., Trial 405-201-00013 or Trial 405-201-00014)

*Open-label Screening/Baseline:* Subjects who completed one of the double-blind phase 3 trials may be eligible to enroll in this trial; subjects who discontinued will not be eligible. Subjects who complete both the 6-week double-blind treatment period and the 7-day follow-up visit are eligible to enroll into this trial. Subjects will be evaluated for eligibility at the 7-day follow-up visit of the double-blind phase 3 trial, and informed consent will be obtained before any procedures for the open-label trial are conducted. Therefore the assessments from the 7-day follow-up visit of the double-blind phase 3 trial may serve as the baseline assessments for the open-label trial.

*Open-label Treatment:* Eligible subjects from the double-blind phase 3 trial will receive daily treatment with open-label centanafadine SR tablets as described in Section 3.2 of the protocol.

During the open-label treatment period, subjects will return to the clinic for evaluations at the end of Weeks 1, 2, 4, 8, 12, 16, 20, 26, 32, 38, 44, and 52/ET. A Week 48 visit will be conducted via telephone, web, or other acceptable means of contact.

*Follow-up:* If any subject discontinues the trial early, every effort should be made to complete the early termination (ET) evaluations as soon as possible and, whenever possible, prior to starting any new medication or treatment. All subjects (completers and early withdrawals) will be evaluated for safety during a 10-day follow up (follow-up telephone calls at 1, 3, and 5 days after the last dose of IMP, in-clinic visits 2 and 7 days after the last dose of IMP, and a follow-up telephone call [or web, or other acceptable means of contact] 10 days after the last dose of IMP).

## De Novo Subjects

*Screening and Washout:* De novo subjects must meet the DSM-5 criteria for ADHD (including predominantly inattentive presentation, hyperactive presentation, and combined presentations) as confirmed by the ACDS Version 1.2. To confirm that ADHD is the primary diagnosis, the Mini International Neuropsychiatric Interview (MINI) will be used to identify and exclude other psychiatric conditions.

Subjects will be screened to establish eligibility for trial participation. The length of screening (Day -28 to Day -2) will include a washout period (if needed), which will range from 7 to 28 days. The investigator or his/her designee must obtain informed consent from the subject prior

to any trial-related procedures being performed. An identification (ID) number will be assigned for each subject with documented consent. Those subjects who meet eligibility requirements will undergo ADHD medication washout, if applicable. If subjects are taking disallowed medications and are able to taper appropriately and safely, they will do so during the screening period. If medication taken is for ADHD, a minimum of 7 days off stimulants and 21 days off nonstimulants will be required before baseline. A complete washout schedule, including common excluded medications and herbal preparations, is provided in Table 4.1-1 of the protocol. The screening visit may take place over multiple days to accommodate the subject's schedule, if needed.

*Baseline:* Following medication washout, subjects will return to the clinic for reassessment of eligibility criteria and establishment of baseline measurements. The interval between the first day of the screening visit (informed consent date) and the baseline visit (Day -1) must not exceed 28 days. Subjects who meet relevant entry criteria by the time they leave the clinic on the day of the baseline visit will be dispensed the trial medication.

CCI

*Open-Label Treatment:* After completing the baseline assessments, eligible subjects will receive daily treatment with open-label centanafadine SR tablets during the open-label treatment period, as described in Section 3.2 of the protocol.

During the open-label treatment period, subjects will return to the clinic for evaluations at the end of Weeks 1, 2, 4, 8, 12, 16, 20, 26, 32, 38, 44, and 52/ET. A Week 48 visit will be conducted via telephone, the web, or other acceptable means of contact.

*Follow-up:* If any subject discontinues the trial early, every effort should be made to complete the Week 52/ET evaluations as soon as possible and whenever possible prior to starting any new medication or treatment. All subjects (completers and early withdrawals) will be evaluated for safety during a 10-day follow up (follow-up telephone calls at 1, 3, and 5 days after the last dose of IMP, in-clinic visits 2 and 7 days after the last dose of IMP, and a follow-up telephone call [or web, or other acceptable means of contact] 10 days after the last dose of IMP).

Late rollover subjects (i.e., those who were unable to rollover from Trial 405-201-00013

or Trial 405-201-00014 due to the inability of an in-person baseline visit in

Trial 405-201-00015) will follow the de novo path (see details in the protocol addendum).

See Figure 3-1 and Figure 3-2 for schematics of the trial design for rollover and de novo subjects, respectively.

Baseline (7-day follow-up visit for Trial 405-201-00013 or Trial 405-201-00014)	Open-label Treatment Period	Follow-up Period
Eligible rollover subjects who completed one of the double-blind phase 3 trials (ie, Trial 405-201-00013 or Trial 405-201-00014) and would potentially benefit from treatment with centanafadine SR for adult ADHD per investigator	Open-label Centanafadine SR 400 mg (TDD)	
Screening/baseline values will be derived from the double-blind phase 3 trials (ie, Trial 405-201-000013 or Trial 405-201-00014), as required	Weeks 1, 2, 4, 8, 12, 16, 20, 26, 32, 38, and 44: clinic visits Week 48: telephone, web, or other means of contact (unscheduled visits as necessary) Day 1 First dose	
 
Safety follow-up on 1, 2, 3, 5
 
7, and 10 days after the last dose of IMP
 
1-day, 3-day, and 5-day follow-up: telephone
 
2-day and 7-day follow-up: clinic visits
 
10-day follow-up: telephone, web, or other means of contact
 

Da Base	I y -1 eline	Week 52/ET

Trial Design Schematic - Rollover Subjects from Trial 405-201-00013 or Trial 405-201-00014 rigure 5.1

Confidential - Proprietary Information

8

15 September 2021

Until the information herein is released by Otsuka to the public domain, the contents of this document are Otsuka confidential information and should not be duplicated or re-distributed without prior written consent of Otsuka.

Screening Period		Open-label Treatment Period	Follow-up Period
Eligible de novo subjects who could potentially benefit from treatment with centanafadine SR for ADHD per investigator		Open-label Centanafadine SR 400 mg/day (TDD)	
One or more visits as needed (Days -28 to -2)	Day 1 First dose	Weeks 1, 2, 4, 8, 12, 16, 20, 26, 32, 38, and 44: clinic visits Week 48: telephone, web, or other means of contact (unscheduled visits as necessary)	Safety follow-up on 1, 2, 3, 5, 7, and 10 days after the last dose of IMP • 1-day, 3-day, and 5-day follow-up: telephone • 2-day and 7-day follow-up: clinic visits • 10-day follow-up: telephone, web, or other means of contact
Da Bas	ay -1 seline		Week 52/ET

Figure 5.1 Trial Design Schematic - De Novo Subjects

9

Until the information herein is released by Otsuka to the public domain, the contents of this document are Otsuka confidential information and should not be duplicated or re-distributed without prior written consent of Otsuka.

# 4 Sample Size and Power Justification

The sample size is not based on statistical power considerations but on ICH/GCP requirements. The trial population will be derived from eligible subjects from the doubleblind phase 3 trial (i.e., Trial 405-201-00013 or Trial 405-201-00014) and de novo subjects from selected sites. It is expected that approximately 560 completing rollover subjects from double-blind phase 3 trial (Trial 405-201-00013 or Trial 405-201-00014) and approximately 145 de novo subjects will be enrolled into this trial.

# 5 Data Sets for Analysis and Missing Data

## 5.1 Data Sets for Analysis

The following samples are defined for this trial:

- Enrolled Sample, which comprises all subjects who sign an eICF for the trial;
- Safety Sample, which comprises all subjects that will receive at least 1 dose of IMP;
- Efficacy Sample, which comprises those subjects in the Safety Sample who have at least 1 post baseline efficacy evaluation of AISRS Total Score

The observed case (OC) dataset will consist of the actual observations recorded at each visit and will be used to present summaries per trial week.

The last-observation-carried-forward (LOCF) data set will include data recorded at a given visit in the Treatment Phase or, if no observation is recorded at that visit, data carried forward from the previous visit in the Treatment Phase. Data collected prior to or on the first day of Treatment Phase dosing will not be carried forward or averaged with Treatment Phase data to impute missing values for the LOCF data set.

## 5.2 Handling of Missing Data

In order to assess the sensitivity of results due to missing data, 2 types of analyses will be performed: last observation carried forward (LOCF) and observed cases (OC). The OC dataset will consist of the actual observations recorded at each visit. The LOCF dataset will include data recorded at a scheduled visit, i.e., all OC data, or, if no observation is recorded at that visit, data will be carried forward from the previously scheduled visit. Baseline data will not be carried forward to impute missing values for the LOCF dataset. The OC dataset will be used for analyses at each trial visit and the LOCF dataset will be used for analyses at the last visit.

# 6 Study Conduct

Late rollover subjects will contribute as de novo subjects in the analyses as they could not rollover to 405-201-00015 due to the COVID-19 pandemic and they will follow the de novo path as described in the protocol addendum.

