| | NOTE: In addition, subjects should be excluded if they have any other abnormal laboratory tests, vital sign results, or ECG findings which in the investigator's judgment are medically significant and that would impact the safety of the subject or the interpretation of the trial results. Tests with abnormal results should be repeated to ensure reproducibility of the abnormality before excluding a subject based on the criteria noted above. |
| 18. | Subjects with hypothyroidism or hyperthyroidism (unless condition has been stabilized with |
| | medications for at least the past 90 days) or an abnormal result for free T ₄ at screening (free T ₄ is measured only if result for TSH is abnormal). |
| · | |

Confidential - Proprietary Information

38

| Tab | le 3.4.3.2-1 Exclusion Criteria for De Novo Subjects |
|-----|--|
| 19. | Subjects receiving any of the prohibited medications within the specified period prior to the first dose of trial medication or who would be likely to require prohibited concomitant therapy during the trial (Section 4). |
| 20. | Subjects with a history of prior exposure to centanafadine. |
| 21. | Subjects with a history of dermatologic adverse reactions or anaphylaxis secondary to drug exposure. |
| 22. | Subjects with HIV seropositive status/acquired immunodeficiency syndrome, seropositive status for hepatitis B (ie, HBsAg positive), or hepatitis C (ie, anti-HCV positive and HCV RNA positive). |
| 23. | Subjects who have previously been enrolled in this trial and subsequently withdrawn. |
| 24. | Subject has participated in a clinical trial involving either an investigational medication or a non-medication intervention within the last 60 days prior to screening or has participated in more than 2 clinical trials involving either an investigational medication or non-medication intervention within the past year. |
| 25. | Any subject who, in the opinion of the investigator, should not participate in the trial. |

See Section 3.9 for details regarding screen failures.

Nonchildbearing potential is defined as male and female subjects who are surgically sterile (ie, male subjects who have undergone bilateral orchidectomy and female subjects who have undergone bilateral oophorectomy or hysterectomy) and female subjects who have been postmenopausal for at least 12 consecutive months.

Subjects must agree to restrictions to medications and lifestyle as described in Section 4.

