3.7.1.1.2 De Novo Subjects

De novo subjects did not participate in Trial 405-201-00013 or Trial 405-201-00014; therefore, they must attend separate screening and baseline visits to allow for completion of eligibility assessments and washout of prohibited concomitant medications, if applicable (Table 3.7-3).

3.7.1.1.2.1 Screening

For de novo subjects, the screening period begins after informed consent has been obtained and will take place between Day –28 and Day –1 prior to enrollment (Visit 1). Although the screening period continues up to administration of the first dose of IMP, screening procedures should be initiated with a sufficient amount of time allotted in order to obtain laboratory results and ECG results from the central reader prior to dosing. Completion of screening activities may require more than 1 visit. All procedures outlined for screening in the Schedule of Assessments (Table 3.7-3) will be performed. Screening evaluations will include the following:

- An assessment of all inclusion and exclusion criteria will be made to determine the subject's eligibility for the trial.
- Demographic data will be recorded.
- Medical and psychiatric history will be recorded, including the DSM-5 diagnosis of ADHD using the ACDS Version 1.2 and MINI will be administeered to rule out other comorbid diagnoses.
- The investigator (or qualified designee) will complete the "Baseline/Screening" C-SSRS form.
- A physical examination including height measurements will be performed.
- Vital sign measurements will be recorded. See Table 3.4.3.2-1 for exclusions based on outcome of screening vital sign measurements.
- A standard 12-lead ECG will be performed after the subject has been supine and at rest for at least 5 minutes. The ECG is to be completed before any blood is drawn.

Confidential - Proprietary Information

- Blood samples will be collected for clinical laboratory tests, including hematology and serum chemistry (with HbA₁c and TSH and T₄). Blood will be drawn after a minimum 8-hour fast, if at all possible (see Section 3.7.4.2). See Table 3.4.3.2-1 for exclusions based on outcome of screening clinical laboratory tests. Vital sign and ECG assessments should be completed before any blood samples are collected.
- Blood samples will be drawn for HIV serology and the presence of HBsAg and anti-HCV.
- Alcohol testing will be conducted via a blood test or using a breathalyzer.

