2.4 Guidance to Record Adverse Events and Discontinuations Due to COVID-19

If a subject tests positive OR is presumed positive with COVID-19, the subject must be discontinued from the trial and an adverse event (AE) of "Coronavirus Infection" OR "Coronavirus Positive Test Result" should be recorded on the AE page of the electronic case report form. A positive test result or a presumed positive subject is not automatically a serious adverse event (SAE), unless an SAE criterion is met (eg, hospitalization).

Confidential - Proprietary Information

12

If a subject discontinues due to COVID-19 either because the subject tests positive OR is presumed positive with COVID-19, then the primary reason for discontinuation should be reported as "Adverse Event" and indicate the AE number in the "Specify the reason for discontinuation" space that corresponds with the AE of "Coronavirus Infection" OR "Coronavirus Positive Test Result." Be sure to remember to enter an AE in the AE form for the "Coronavirus Infection" OR "Coronavirus Positive Test Result."

If a subject discontinues due to COVID-19 other than the subject testing positive OR being presumed positive with COVID-19, then the primary reason for discontinuation should be reported as "Other." Be sure to specify the reason as "COVID-19" followed by the reason ensuring that the prefix of the description includes "COVID-19." Do note that the reason "Other" should be selected even if the subject decides to withdraw consent or if the investigator decides to withdraw the subject due to COVID-19 concerns.

2.5 **Statistical Analyses**

Any impact of COVID-19 on the planned statistical analyses for the trial will be described in the final statistical analysis plan.

3 **Trial Population**

3.1 **Inclusion Criteria**

Late rollover subjects (ie, those who were unable to rollover from Trial 405-201-00013 or Trial 405-201-00014 due to the inability of an in-person baseline visit in Trial 405-201-00015) are required to meet the inclusion criteria presented in Table 3.1-1.

| Tabl | Table 3.1-1 Inclusion Criteria for Late Rollover Subjects From | | | | | | | |
|------|---|--|--|--|--|--|--|--|
| | Trial 405-201-00013 or Trial 405-201-00014 | | | | | | | |

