| 1. | Subjects who completed or were administratively early terminated from the double-blind phase 3 trial (ie, Trial 405-201-00013 or Trial 405-201-00014) within the period restricting rollover due to the COVID-19 pandemic and who, in the opinion of the investigator, could potentially benefit from centanafadine for ADHD. | | | | | | | |
| 2. | Subjects who are able to complete the consent process and/or consent obtained from a legally acceptable representative (as required by the IRB) prior to the initiation of any protocol-required procedures. | | | | | | | |
| 3. | Subjects who, during the double-blind trials, demonstrated adequate compliance with medication and protocol requirements, per the investigator's judgment. | | | | | | | |
| 4. | Ability, in the opinion of the principal investigator, to understand the nature of the trial and follow protocol requirements, including the prescribed dosage regimens, tablet ingestion, and discontinuation of prohibited medications, and to read and understand the written word in order to be reliably rated on assessment scales. | | | | | | | |
| 5. | Subjects who are willing to discontinue all prohibited psychotropic medications (refer to Section 4.1 of the protocol) starting from the time of signing the informed consent and up to the 10-day safety follow-up period. | | | | | | | |

IRB = institutional review board.

Confidential - Proprietary Information

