3.2 Exclusion Criteria

Late rollover subjects (ie, those who were unable to rollover from Trial 405-201-00013 or Trial 405-201-00014 due to the inability of an in-person baseline visit in Trial 405-201-00015) will be excluded if they meet any of the exclusion criteria presented in Table 3.2-1.

| Tab | le 3.2-1 Exclusion Criteria for Late Rollover Subjects From Trial 405-201-00013 or Trial 405-201-00014 |
|-----|--|
| 1. | Subjects who, during the double-blind phase 3 trial (ie, Trial 405-201-00013 or Trial 405-201-00014), experienced, in the opinion of the investigator, poor tolerability to the IMP or whose safety assessments resulted in new concerns that would suggest the subject may not be appropriate for a 52-week treatment with IMP. |
| 2. | Subjects who have demonstrated noncompliance, based on the investigator's judgment, to follow trial procedures during the course of their participation in the double-blind phase 3 trial (ie, Trial 405-201-00013 or Trial 405-201-00014). The medical monitor should be contacted if the investigator is unsure of a subject's eligibility. |
| 3. | Females who have a positive pregnancy test result prior to receiving IMP. |
| 4. | Sexually active males or FOCBP who do not agree to practice 2 different methods of birth control or remain abstinent during the course of the trial and for 30 days after the last dose of IMP for female subjects, and 90 days after the last dose of IMP for male subjects and their partners who are FOCBP. Unless the subject is sterile (ie, females who have had a bilateral oophorectomy or hysterectomy or who have been postmenopausal for at least 12 consecutive months; or males who have had a bilateral orchiectomy) or remains abstinent, 2 of the following precautions must be used: vasectomy, tubal ligation, vaginal diaphragm, intrauterine device, birth control pills, birth control injection, birth control implant, birth control patch, condom with spermicide, or sponge with spermicide. Male subjects who do not agree to refrain from donating sperm from screening through 90 days after the last dose of IMP will also be excluded. |

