## 9 Safety Analysis

The primary safety endpoint analysis is the frequency and severity of AEs in the open-label treatment period (see Section 9.1). Other standard safety variables to be analyzed include clinical laboratory tests, vital signs, body weight, waist circumference, BMI, 12-lead electrocardiograms (ECGs), and physical examinations. In addition, data from the following safety scales will be evaluated: C-SSRS and Study Medication Withdrawal Questionnaire (SMWQ).

Safety analyses will be conducted based on the Safety Sample, and summary statistics will be provided by parent study treatment group for rollover subjects, de novo subjects and overall, unless otherwise indicated.

Unless otherwise specified, in general, analysis of safety data will be performed on observed case and for last visit.

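### The SAP reports late rollovers in the de novo column, and its TEAE wording counts baseline events that the protocol would not

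*SAP*

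**What the plan says.** **Late rollovers.** These are parent-trial subjects who could not enter on time because an in-person baseline visit was impossible. SAP 6 rules: "Late rollover subjects will contribute as de novo subjects in the analyses". SAP 3 and SAP 6 both explain that they follow the de novo path. SAP 9 presents safety summaries "by parent study treatment group for rollover subjects, de novo subjects and overall", and disposition, baseline and efficacy summaries use the same columns.

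Protocol 3.7.1.1.2 says of the de novo group: "De novo subjects did not participate in Trial 405-201-00013 or Trial 405-201-00014". Table 3.4.3.2-1 excludes from it "Subjects with a history of prior exposure to centanafadine" (exclusion 20) and anyone who was in an interventional trial "within the last 60 days prior to screening" (exclusion 24).

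The COVID-19 Addendum gives late rollovers their own criteria. Table 3.1-1 admits "Subjects who completed or were administratively early terminated from the double-blind phase 3 trial", within the period when rollover was restricted. Table 3.2-1, exclusion 1, removes those who, in the parent trial, "experienced, in the opinion of the investigator, poor tolerability to the IMP". Addendum 2.5 passes the analysis question to the SAP: "Any impact of COVID-19 on the planned statistical analyses for the trial will be described in the final statistical analysis plan".

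**TEAE definition.** Protocol 7.4.1 and the synopsis count an AE already reported at baseline only if it increases in intensity, becomes serious or drug-related, or leads to death or to stopping, interrupting or reducing IMP. SAP 9.1 opens with a narrower rule, onset on or after first dose. Its next sentence adds events continuing from baseline that were worsening, serious or drug related, or that had those same outcomes.

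**The concern.** The reporting columns are built on parent-trial history, but late rollovers are placed by visit schedule. A reader will take the de novo column as the safety experience of people new to the drug. It would also contain people who had been in a parent trial, some of them probably pre-exposed to centanafadine and passed as having tolerated it. Early tolerability findings are where such a filter would show most. Protocol 1.3 reports that rash led to discontinuation for 5 subjects in a phase 2 trial, and skin eruptions are the AESI here.

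The TEAE wording concerns the primary endpoint itself. A programmer following the SAP's second sentence could produce different counts from one following the protocol, or from one following the SAP's own first sentence.

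**Working it through.** The plan states no figure for either point, so there is none to reproduce. The check is a comparison of texts, followed by illustrations on assumed inputs.

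**1. Which group do late rollovers resemble?**

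| Feature | De novo (protocol) | Late rollover (addendum) |
|---|---|---|
| In a parent trial | No | Yes, by definition |
| Prior centanafadine | Excluded | Not excluded |
| Interventional trial in prior 60 days | Excluded | Not excluded |
| Screened on tolerability in the parent trial | Not applicable | Yes |
| Separate screening and baseline visits | Yes | Yes |

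The 12 exclusions in Addendum Table 3.2-1 contain neither de novo exclusion 20 nor 24. Some rollovers must have taken centanafadine, because Protocol 4.1 has rollovers washing out from it. The SAP's other COVID-19 provisions are displays by visit type (SAP 8.1 for AISRS, and a table of face-to-face and virtual visits in SAP 12). Nothing in the SAP 12 list isolates late rollovers.

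**2. Size of the mixing (illustrative).** From the documents: about 145 de novo subjects expected (Protocol 7.1, SAP 4). Assumed: number of late rollovers L; share f of them who had centanafadine; AE-discontinuation rate p = 15% in naive subjects (including parent-placebo late rollovers) and q = 5% in pre-exposed subjects.

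- Share of column = L / (145 + L)
- Column rate = [145p + L(fq + (1 − f)p)] / (145 + L)

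| L | Share | f = 1 | f = 0.5 | f = 0 |
|---|---|---|---|---|
| 15 | 15/160 = 9.4% | 22.50/160 = 14.06% | 23.25/160 = 14.53% | 15.0% |
| 30 | 30/175 = 17.1% | 23.25/175 = 13.29% | 24.75/175 = 14.14% | 15.0% |
| 60 | 60/205 = 29.3% | 24.75/205 = 12.07% | 27.75/205 = 13.54% | 15.0% |

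The shift is f × share × (p − q), so other rate pairs scale directly. At L = 60 and f = 1, 10% against 5% gives 8.5% instead of 10%, and 60% against 40% gives 54.2% instead of 60%.

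**3. The two TEAE tests.** Take an AE judged related in the parent trial, recorded at the open-label baseline, and unchanged afterwards.

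- Protocol 7.4.1: no rise in intensity, nothing newly serious or related, no listed outcome. Not a TEAE.
- SAP 9.1, first sentence: onset before first dose. Not a TEAE.
- SAP 9.1, second sentence: continuing from baseline and drug related. A TEAE, and also a related TEAE.

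An unchanged serious event passes the second sentence in the same way. The route exists: Protocol 3.7.1.1.1 and Table 3.7-1, footnote c, allow adverse-event information from the parent trial's 7-day follow-up visit to serve for the open-label baseline. They permit this and do not require it.

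**4. Size of the TEAE effect (illustrative).** From the documents: about 560 rollovers. Assumed: 1% to 3% enter with a recorded ongoing related AE that stays unchanged, and 40% to 60% of those have a genuine TEAE anyway.

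- Subjects meeting the clause: 560 × 0.01 = 5.6 to 560 × 0.03 = 16.8, about 6 to 17.
- Net additions to the any-TEAE count: 5.6 × (1 − 0.6) = 2.2 to 16.8 × (1 − 0.4) = 10.1, about 2 to 10.
- Against 560 + 145 = 705 expected subjects: 2.2/705 = 0.3% to 10.1/705 = 1.4%.

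**The case against.** On late rollovers, the rule is prespecified, openly stated and explained, and the addendum had left the matter to the SAP. These subjects do share features with de novo subjects: full rescreening including ACDS and MINI, and the same visit numbering. They also differ from ordinary rollovers, who enter directly at the 7-day follow-up visit and are excluded if they restarted ADHD therapy in that week. De novo exclusions 20 and 24 do not govern late rollovers, so no eligibility rule is broken. No test or comparison between columns is planned. The tolerability exclusion rests on investigator opinion, and for a parent-placebo subject it says nothing about tolerating centanafadine.

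Most of this stands and limits the weight of the point. It shows that neither existing group fits well, which is a reason to show late rollovers apart. Disclosing the rule does not let a reader separate the two populations, and rescreening does not undo prior exposure.

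On TEAEs, the SAP wording looks like compressed drafting: it lists the protocol's triggers with a shortened verb. The affected case also needs several conditions together. The AE must outlast at least a week off drug, must not have barred entry, must be recorded at baseline with its related status kept, and must then stay unchanged. AE recording for this trial starts at its own consent, and an event before dosing has no temporal link to open-label IMP. The case may therefore be rare. The wording still departs from the protocol without saying so and conflicts with the sentence before it.

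**Conclusion.** Both points hold and should be fixed; confidence is medium because the sizes are unknown.

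The late-rollover rule conflicts with the protocol's meaning of de novo and blurs that column in every summary that uses it, while leaving the overall column unchanged. Its effect depends on how many late rollovers there were and what they received in the parent trial, and the documents give neither. It is zero in the illustration if all had placebo.

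The TEAE clause is wrong as worded. Applied literally, it can only raise primary-endpoint counts relative to the protocol. The illustrated 2 to 10 extra subjects rest wholly on assumed frequencies. Neither point is shown to change the overall safety conclusion.

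**What to change.** **SAP 6.** Flag late rollovers and limit the de novo column to subjects never enrolled in Trial 405-201-00013 or 405-201-00014. Show late rollovers in their own column, by parent treatment if numbers allow. At minimum, show the de novo column with and without them, and report how many there are.

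**SAP 9.1.** Replace the two sentences with one definition that matches the protocol. An AE present before the first open-label dose is a TEAE only if, after that dose, it worsens, becomes serious or drug-related, or results in death or in discontinuation, interruption or reduction of IMP.

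The cost is one grouping flag, one extra column or with/without display, and one rewritten sentence. No new data are needed, since parent treatment is already used for ordinary rollovers. The drawback is that a late-rollover column may be small and imprecise.
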